- There is limited evidence in animal models of cancer suggesting treatment with NAD+ boosting compounds could increase cancer cell proliferation and exacerbate cancer progression and metastasis; however, in other studies, NAD+ precursors have been shown to have favorable effects on metabolism that prevent or limit cancer growth²¹.
- A recently conducted Phase-1 clinical trial in humans (Trammel et al., Nat Commun. 2016) found that NR was safe for human consumption and reported no serious adverse effects at doses ranging from 100 – 1,000mg²².
 Table 3. Treatment emergent adverse events from
- Data from our own recently published randomized, placebo-controlled crossover pilot study of long-term dosing in 24 healthy older adults²³. indicate no serious adverse events (*Table 3*) associated with the proposed dose (500 mg, 2x/day), and no change in markers of liver or renal function²³.

Rationale for Proposed Treatment Dose, Duration and Frequency

 Bioavailability. Because NR is directly taken up by cells and metabolized into NAD⁺ and related metabolites, NAD⁺ has proven to be undetectable in the plasma.

pilot study. Based on N=30 randomized subjects				
Adverse Event	Placebo	NR		
Headache	4	0		
Nausea	0	1		
Skin Rash	1	1		
Flushing/Hot flashes	2	1		
Fainting	1	0		
Drowsiness	1	0		
Leg cramps	0	1		
Increased Bruising	0	1		

Data represent number (n) of times AE was reported. Number of subjects reporting AEs (n=7); Number of subjects reporting \geq 2 AE (n=5). As such, assessment of the NAD⁺ metabolome in peripheral blood mononuclear cells (PBMCs) has emerged as the gold standard method of evaluating NAD⁺ bioavailability in response to supplementation with NAD⁺ boosting compounds^{22,23}. During a recently published Phase I clinical trial with NR in 12 healthy adults (Trammel et al., Nat. Comm. 2016), the concentration of NAD⁺ and related metabolites were dose-dependently elevated in PBMCs compared with baseline following a single ingestion of 100, 300, and 1000 mg NR²².

- Rationale for Dose and Duration. For the present study, we have chosen to study a dose of 500mg, 2x/day (i.e., 1,000 mg/day) for 12 weeks. We have chosen to standardize the dose among subjects, rather than administer NR in relation to body mass in order to increase the translational potential of the proposed work, as formulation of a treatment based on body mass is impractical in a clinical setting. The rationale for this dose and treatment duration is based on:
 - Preclinical studies using NR in mice demonstrating efficacy for improving physiological function (e.g., insulin sensitivity, mitochondrial biogenesis, fatty acid oxidation) with doses ranging from 250-400 mg/kg/day, which translate to an equivalent dose in humans of between 1,200 – 2,000 mg/day for an average 60kg adult;
 - Results of a phase I clinical trial demonstrating an increase in NAD⁺ and related metabolites at this dose in healthy humans (*Appendix, Figure 1*);
 - The PI's own pilot study (clinicaltrials.gov registry: NCT2921659) demonstrating efficacy of this dose for improving measures of arterial stiffness and blood pressure in healthy (cognitively normal) middle-aged and older adults with a shorter duration than the proposed study;
 - At least 2 other clinical trials in healthy or obese individuals using a similar dose (NCT02300740, NCT02303483).
- **Rationale for Frequency of Doses.** Subjects will be advised to consume NR or placebo pills twice a day (one dose in the morning and one in the evening) in order to maintain elevated circulating NAD+ levels and to lower the risk of potential side effects caused by a larger single dose. The exception to this will be in the morning of testing, in which subjects will not take their morning dose until completion of the testing session in order to avoid any acute effects of the compound on the proposed outcomes. Subjects will be advised to take pills with food in order to a) maximize absorption; b) increase subject adherence by timing pill intake with meals; and c) decrease risk of nausea or GI discomfort.

Description of Placebo Capsules. The placebo capsules contain microcrystalline cellulose within vegetarian capsules. The appearance is a blue powder within a blue capsule.

Investigational New Drug Application. In addition to the details above related to the safety of NR supplementation in humans, we have also received Investigational New Drug (IND) status from the Food and Drug Administration (CDER Division of Neurological Products) for the use of NR in patients with MCI (IND#:135449).

ADMINISTRATION, ADHERENCE AND SUBJECT MONITORING

Intervention Administration. Placebo or NR capsules will be packaged and distributed by ChromaDex Inc. (under trade name, NIAGEN®) in individual containers. 12 weeks' worth of capsules will be administered to subjects by the research team at the beginning of the trial. Subjects will be provided with explicit instructions for dosing and frequency including instructions for missed doses.

Monitoring Adherence (pill count). Subjects will be instructed to bring their used and unused pill containers to the last post visit and, at which time a member of the research team will count the number of pills remaining in the container to assess adherence to the intervention.

Plan for Monitoring Adverse Events (AE's) and Serious Adverse Events (SAE's)

Adverse Event (AE): any untoward or unfavorable medical occurrence in a human study participant, including any abnormal sign (e.g. abnormal physical exam or laboratory finding), symptom, or disease,

temporally associated with the participants' involvement in the research, whether or not considered related to participation in the research.

Adverse Event Recording

The period for recording AE's will begin at the time of informed consent and will end at the time that the participant completes all testing, or is withdrawn from the trial. At each in-person or phone check-in, a blinded member of the study team will seek information from the participant on adverse events by specific questioning using a standardized physical symptom survey. Information on all AE's reported during the study period will be recorded immediately in the case report form (CRF). Adverse events will be described by duration (start and stop dates and times), severity, outcome, treatment and relation to study drug, or if unrelated, the cause, as described in the Data and Safety Monitoring Plan (DSMP).

Serious Adverse Event (SAE): any adverse event that:

- Results in death;
- Is life threatening, or places the participant at immediate risk of death from the event as it occurred;
- Requires or prolongs hospitalization;
- Causes persistent or significant disability or incapacity;
- Results in congenital abnormalities or birth defects;
- Is another condition which investigators judge to represent significant hazards.

If a SAE occurs while the participant is on campus for a scheduled visit, the participant will be sent to the Christiana Care Medical Aid Unit ("Urgent Care") on the STAR Campus. If a participant contacts the laboratory or PI prior to seeking treatment for an ongoing AE or SAE, the participant will be directed to seek immediate medical treatment (e.g., visit their primary healthcare provider or, if requiring immediate attention, the nearest Urgent Care facility or Emergency Department). Any participant who is experiencing a life-threatening **medical emergency** will be instructed to call 911.

Reporting of SAE's

All participants experiencing a SAE will be instructed to notify the principal investigator after seeking immediate medical attention. As detailed in the Data and Safety Monitoring Plan (DSMP), all SAE's will be reported to the IRB, DSMB and other regulatory bodies (e.g., FDA, NIH) within 24 hours of the event being reported to the investigator. An expedited report of the SAE can be submitted by telephone, fax, or email and will be followed by a detailed, written SAE report as soon as possible. In the event that a participant calls the PI or another member of the study team prior to receiving treatment for an ongoing SAE, that participant will be instructed to seek immediate medical attention (e.g., visit urgent care).

Unblinding in Response to a SAE

All participants will be given a "Clinical Trial Participant Card" at the time of informed consent, which will provide the dates of their anticipated involvement in the study and important details regarding the active compound under investigation. The card will also provide a QR code to access the clinicaltrials.gov registry for this trial. Participants will be instructed to keep this card with them at all times (e.g., in their wallet) and to provide it to emergency personnel or other healthcare professionals if seeking treatment for an AE or SAE. In the event that emergency personnel or other healthcare professionals responding to a SAE determine that it is *medically necessary* to know the treatment to which a participant is randomized, the card will provide the contact information for the PI's office. PI will program their office line to forward all calls to their personal phone outside of normal business hours. In case of an emergency, the PI will be capable of breaking the blind for that participant.

STUDY TIMELINE

Experimental sessions (baseline & follow-up) will be conducted over a 7 day period. The order of these visits may be switched as needed in order to facilitate scheduling. Subjects will continue their treatment (NR or placebo pills) until experimental sessions for each condition are completed; however, subjects will

be instructed to refrain from taking study pills within 24 hours of an experimental session, to avoid any confounding effects of acute NR supplementation. In the event of a conflict (e.g., due to scheduling or illness), experimental sessions may be scheduled \pm 7 days from the ideal testing window. We anticipate that the typical time lapse between completion of screening measures and the beginning of the intervention will be no more than 1 week and that the study will take approximately 15 weeks to complete. The study will require 16 hours of the subject's time in the clinical trial.

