		Screening for MCI will occur under a separate protocol and elig be brought in for informed consent and study-specific				
Screening	Week -1	Visit 1	2 hours	Virtual*	Informed Consent & General Screening	
		Visit 1.1	30 minutes	NOVA Lab or LabCorp	Screening Blood Draw	74 mL (~5.0 TBL)
		Randomization Group A: NR or Group B: Placebo				
Baseline Testing	Week 0	Visit 2	3 hours	NOVA Lab	Vascular Testing	
		Visit 3	1.5 hours	Virtual*	Cognitive Testing	
		Visit 4	2 hours	CBBI	Neuronal Testing & Receive Capsules	
	Week 2	10 min Phone Check-In				
ion T	Week 4	Visit 5	0.5 hours	Virtual*	Zoom Check-In	
erventi Period	Week 6	10 min Phone Check-In				
Intervention Period	Week 8	Visit 6	0.5 hours	Virtual*	Zoom Check-In	
	Week 10	10 min Phone Check-In				
Follow-Up Testing	Week 12	Visit 7	3 hours	NOVA Lab	Vascular Testing	60 mL (~4.0 TBL)
		Visit 8	1.5 hours	Virtual*	Cognitive Testing	
		Visit 9	2 hours	CBBI	Neuronal Testing	
	Total Time		16 hours		Total Blood	134 mL (~9.0 TBL)

Brief Overview of Study Visits

not have access to a computer with video conferencing capabilities or upon the participant's request.

research team. All procedures and aspects related to the study including any potential risks will be

described to the subject. The investigator will read the informed consent form to the subject and will answer any questions that the subject may have prior to obtaining the subject's written consent. As documentation of the informed consent, the subject and the investigator performing the consent will sign the consent document and a copy of the signed consent form will be given to the subject. Alternatively, the consent may also be performed online via a private video conference and using the eConsent framework in REDCap. The video conferencing software is HIPAA-compliant and each scheduled online meeting will be secured with private meeting access controls, password protection, and end-to-end encryption so data in transit cannot be intercepted. The ability to provide informed consent will be monitored by the research team throughout the trial. In addition to obtaining written informed consent, all experimental procedures will be re-explained to the subjects at the time that they are performed, and verbal consent will be obtained.

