- **Middle Cerebral Artery Screening:** A research team member will use a transcranial doppler ultrasound probe to examine the temporal window for screening of a visible middle cerebral artery. This is done during the screening visit to simplify the preparation of Visits 2 & 7. The results of this screening test will not impact eligibility for this study.

RANDOMIZĂTION (will occur after VISIT 1.1)

Randomization Procedures. Subjects who qualify for the study based on screening assessments will be randomly assigned by the study coordinator to receive either treatment A or treatment B. The identity of each treatment (i.e., NR or placebo) will be blinded by the manufacturer (ChromaDex, Inc.) and the blinding code will be sent to a member of the PI's department ([name]) who is unaffiliated with this study. [name] will enter the blinding code in a secure REDCap form that will remain hidden from the rest of the study team. The PI will be given a separate login ID and password to access this REDCap form and determine the assigned treatment condition of a subject in the event of an emergency (described below under serious adverse events). A blocked randomization scheme will be uploaded into REDCap by the biostatistician with block size (*b*) resulting in an imbalance of no more than 2 subjects (*b*/2) between group assignments. To address potential imbalance between key biological variables including sex (male vs. female) and APOEε4 status (carriers vs. non-carriers),

the blocked randomization scheme will be stratified such that participants within each strata will be block randomized to either placebo or NR.

Study Restrictions. All experimental visits will be conducted under overnight fasted conditions (no meal within ~12 hours of testing) with the exception of cognitive function and MRI sessions. Participants will be asked to discontinue use of any vitamin B₃-containing supplements (i.e., nicotinamide, niacin, nicotinic acid, nicotinamide riboside, nicotinamide mononucleotide) 2 weeks prior to and throughout participation in the study. Subjects will be asked to refrain from non-prescription medications for 48 hours; alcohol and exercise for 24 hours, caffeine for 12 hours prior to all study visits as these are factors known to modulate vascular function as well as circulating biomarkers of interest. If subjects receive the COVID-19 vaccine, they will not perform any experimental visit until at least one week following vaccination.

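### Two treatment codes (A and B) shared by all participants mean that one emergency look-up can reveal more than one participant's arm

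*Combined protocol and SAP*

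**What the plan says.** The relevant statements are all in the combined protocol and SAP.

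- **Allocation** (section 6, Randomization Procedures). Qualifying participants are "randomly assigned by the study coordinator to receive either treatment A or treatment B". The biostatistician uploads a blocked scheme to REDCap, stratified by sex and APOEε4 carrier status. The block size is described as keeping the imbalance to at most 2, which is written as half the block.
- **What is masked** (same paragraph). The manufacturer conceals which letter is NR. A member of the PI's department who is not part of the study "will enter the blinding code in a secure REDCap form that will remain hidden from the rest of the study team".
- **Who can open it** (same paragraph). The PI receives a login to "access this REDCap form and determine the assigned treatment condition of a subject in the event of an emergency".
- **Intended scope** (section 6, Unblinding in Response to a SAE). "In case of an emergency, the PI will be capable of breaking the blind for that participant".
- **Visit table** (section 6, Brief Overview of Study Visits). The randomization row reads "Randomization Group A: NR or Group B: Placebo".
- **Packaging** (section 6, Intervention Administration). Capsules come in individual containers. No container numbering is described.
- **PI decisions** (section 7). The PI determines final eligibility and judges whether a change of medication ends participation. A serious adverse event that leads to unblinding is itself listed as a reason for exit.

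**The concern.** The SAE text intends a break limited to one person. The randomization text describes a secret that belongs to the whole trial: which of two letters is the active product. Nothing in the documents describes a participant-level code, a numbered container, a form that shows one record only, or masking of the letters from the PI. If the scheme works as written, the first emergency look-up also tells the PI what the letters mean for everyone else.

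What is at stake is the PI's own blinding for decisions still to be made. One is the medication-change exit criterion for people still on treatment. The other is final eligibility, if the next assignment can be guessed from the blocks. The visit table adds a smaller problem: read literally, it prints the link that the randomization text says is concealed.

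**Working it through.** The plan gives no figure to reproduce here. The check is a count of what one look-up discloses.

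**1. Two shared codes.** The possible links are {A = NR, B = placebo} and {A = placebo, B = NR}, so there are 2. Learning one participant's letter and arm leaves 1. Others with the same letter are decoded directly, and the rest by elimination. Everyone whose letter is known is therefore decoded: up to 58 of 58 in the target sample. Section 7 also gives 73 recruited, but the extra 15 include failed screening, so the number randomized lies between 58 and 73.

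**2. More codes per arm** (illustration; the documents do not describe this). With k codes per arm, one look-up directly discloses those who share that code, about 58/(2k).
- k = 2: 58/4 = 14.5 people
- k = 4: 58/8 = 7.25, about 7 people
- one code per participant: 1 person

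**3. Who is still exposed when a break happens.** Participants who have finished week 12 have fixed measurements. Two groups remain.
- *In follow-up.* Section 7 plans about 20 people a year, and section 6 gives 12 weeks of treatment and about 15 weeks in the study. With even recruitment, the number in the study at one time is 20 × 15/52 = 5.8. If only the 58 are counted, the rate is 58/4 = 14.5 a year and the number on treatment is 14.5 × 12/52 = 3.3. The range is about 3 to 6.
- *Yet to enrol.* This depends on timing. For a break halfway through recruitment it is 58/2 = 29 to 73/2, about 36.

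**4. Prediction of upcoming assignments.** If half the block equals 2, the block size is 4. A block holding two of each letter has 6 possible orders.
- The fourth assignment always follows from the first three.
- The third follows from the first two when those match, which happens in 2 of 6 orders, or 1/3.
- On average 1 + 1/3 = 1.33 of every 4 assignments in a stratum can be known in advance.

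This requires knowing the ordered letters within each stratum and the candidate's sex and APOE status. APOE status is determined before randomization. While the link is unknown, a predicted letter says nothing about the arm. After one look-up it does.

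**5. Residual leak with unique codes.** If one participant is unblinded, each of the other three in that block of 4 is in the same arm with probability (2 − 1)/(4 − 1) = 1/3. That hint is confined to at most three people and is not a disclosure.

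**The case against.** Several points count against a stronger reading, and most of them stand.

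- **Only the PI has the login.** The form stays hidden from the rest of the team, adverse events are elicited by a blinded team member, and no section says that the PI administers or scores tests. A reader might infer that one break ends the double blind for the whole trial. The documents do not support that: participants and other staff remain blinded unless the PI tells them.
- **The form may already be a per-participant look-up.** The wording about a single subject fits that design, and individual containers could carry unique numbers. The Data and Safety Monitoring Plan, to which the protocol refers for adverse-event handling, is not available here. This lowers confidence. It does not remove the point, because the randomization text describes two treatments and a code for the identity of each.
- **The PI may not see the letters.** The coordinator assigns them, and the documents are silent on PI access. This also stands. Nothing masks the letters either, and interpreting an A/B code for one participant requires knowing that participant's letter.
- **Eligibility is settled before randomization.** This is true, so knowing past arms does not by itself bias entry. The route is prediction within small blocks, as worked above.
- **The table row may be only a schematic of the two arms.** This is quite possible, and the row is not evidence that the code has leaked. The two places still disagree as written.
- **Breaks may be rare.** The protocol reports no serious adverse events with NR, and outside clinicians must judge the information medically necessary. It is tempting to attach a probability to at least one break over the trial. The documents give no rate from which to derive one, so none is offered. The exit list does foresee unblinding, but removing the affected participant does not re-mask the others.

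**Conclusion.** The point holds in a limited form. As described, the scheme does not deliver the single-participant break that the SAE section intends: one look-up decodes both letters, and with them every participant whose letter the PI knows, up to all 58 to 73. The exposure to bias is narrower than that count. It concerns about 3 to 6 people in follow-up at the time and those still to enrol. It acts through the PI's medication-change judgement and possibly through foreseeable assignments at the eligibility decision.

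The conclusion assumes that the PI can see the A/B assignments and that containers carry no unique numbers; the documents settle neither, so confidence is medium. The prediction route also assumes fixed blocks of 4, which is what the stated imbalance limit implies. No sample size, power or alpha figure is affected. This is an inexpensive improvement that should be made, not a finding that blinding has failed.

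**What to change.** 1. Give each participant, or each container set, a unique code in an order unrelated to arm. The unaffiliated department member who already receives the blinding code holds the code-to-treatment list and converts the biostatistician's scheme to these codes before it goes into REDCap. The coordinator and PI then see only a code, which also closes the block-prediction route.
2. Make the emergency REDCap form show one participant's record at a time and log each access with date and reason. The PI keeps direct emergency access, so no additional out-of-hours cover is needed.
3. Reword the visit-table row so that it does not pair letters with arms, for example: randomized to NR or placebo.
4. If unique numbers, a single-record form or masking of the letters from the PI already exist, state this in Randomization Procedures. The table row is then the main remaining correction.

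The cost is a small labelling effort by the manufacturer or the code holder, outside the blinded team, and some REDCap set-up. Visits, treatment, sample size and analysis do not change.

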7. STUDY POPULATION AND RECRUITMENT

Study Population

58 older adult men and women of all races and ethnic backgrounds between the ages of 60-90 years with cognitive scores indicative of mild cognitive impairment that includes impaired memory function (i.e., "amnestic MCI or "aMCI") will serve as subjects for this study. To account for a 25% subject exclusion rate due to dropout/experimental failure, failed screening or conversion to dementia (15 subjects), a total of 73 patients with aMCI (~20 subjects/year over 4 years) will be recruited for this study in order to meet our enrollment goal.

Recruitment and Screening

Participants for this study will be recruited through the "Screening eligibility of older adults to participate in clinical trials related to memory" study (UD IRB #1318668), which is being conducted by [name] and [name]. Participants will be primarily recruited through posted flyers and direct mailings targeted towards older adults with a self-report of memory complaints. Additional subjects will be recruited through the Swank Memory Center for Memory Care and Geriatric Consultation ("Swank Memory Center") in Wilmington, DE in collaboration with co-investigator, [name]. Specific details regarding subject recruitment are described in the screening protocol. Briefly, subjects will undergo a brief modified telephone pre-screening for cognitive status (TICS-m) and those qualified will undergo a more comprehensive in person cognitive evaluation with a research nurse. Individuals with memory scores indicative of amnestic MCI that express interest in participating in this study will be recruited for enrollment into this clinical trial by the study coordinator. Additionally, this study will be listed on the Alzheimer's Prevention Registry.

Final eligibility will be determined by the PI based on the inclusion/exclusion criteria stated below:

Inclusion Criteria

- Cognitive function scores consistent with amnestic mild cognitive impairment based on prescreening evaluation;
- age 60-90 years;
- MMSE score >21 at time of initial consent;

Exclusion Criteria

- blood chemistries indicative of abnormal renal, liver, thyroid and adrenal function; estimated glomerular filtration rate using the MDRD prediction equation must be ≥30 ml/min/1.73 m²;
- any clinically significant abnormal blood chemistry values as determined by the NMPCC nurse practitioner;

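### The randomization section lets blocks of 4 be deduced, and the coordinator who recruits also assigns codes A and B, so about 30% of codes could be foreseen; the balance limit of 2 holds only within a stratum

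*Combined protocol and SAP*

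**What the plan says.** All of the design facts are in Section 6 (Randomization Procedures) and Section 7 (Recruitment and Screening).

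- **Block size.** The scheme has one block size, *b*, "resulting in an imbalance of no more than 2 subjects" between the groups, and the text gives this limit as *b*/2. Neither a varying size nor a rule for hiding the size is mentioned.
- **List.** "A blocked randomization scheme will be uploaded into REDCap by the biostatistician".
- **Assignment.** Qualifying subjects "will be randomly assigned by the study coordinator to receive either treatment A or treatment B". The manufacturer masks what A and B stand for. The key sits in a REDCap form hidden from the team, except for an emergency login given to the PI.
- **Recruitment.** People identified by the separate screening protocol are "recruited for enrollment into this clinical trial by the study coordinator".
- **Eligibility.** "Final eligibility will be determined by the PI".
- **Strata.** For sex and APOE ε4 status, "the blocked randomization scheme will be stratified such that participants within each strata will be block randomized". Genotype comes from the screening blood draw and is known before randomization.
- **Later contact.** The coordinator also runs check-ins that include the physical symptom survey (Section 6, Visits 5 & 6).

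**The concern.** Concealed allocation means that nobody who influences entry can tell what the next assignment will be. A hidden list is not enough for that if the next entry can be worked out from earlier ones. With blocks of known size 4, once two As or two Bs have been used in a block, the remaining places are forced. The coordinator issues the codes and so sees the history.

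The risk is selection. If staff came to believe that one letter was active, a foreseeable code could affect whether or when a borderline candidate was put forward. As the text reads, A and B are common to all participants, so one emergency unblinding would decode both letters for whoever learned the result. In a trial of 58, a few selectively entered participants could matter.

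Separately, the limit of 2 is stated for the group assignments as a whole, while the blocking is done separately in each stratum. The limit does not carry over to the total.

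**Working it through.** **Inputs**
- *b*/2 = 2, so *b* = 4 (Section 6). Assumption: every block has this size.
- Sex (2 levels) × APOE ε4 status (2 levels) = 4 strata, if crossed (Section 6).
- Planned size 58 (Section 7), so 58/4 = 14.5, or about 15 per stratum if shares are equal. The documents give no stratum shares. I assumed 25/25/25/25, 30/30/20/20 and 36/24/24/16%.

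**The plan's own figure.** Among the six arrangements of two As and two Bs, the largest running difference is 2 = *b*/2. The stated limit is reproduced for a single block sequence, that is, within one stratum.

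**Codes known with certainty, blocks of 4.** AABB and BBAA each force two places, and the other four arrangements force one each.
- Complete blocks: (2×2 + 4×1)/6 = 8/6 = 1.33 of 4 = 33.3%.
- By position in the block, the chance of certainty is 0, 0, 1/3, 1.
- With 15 in a stratum (three full blocks plus three places): (3×1.333 + 1/3)/15 = 4.333/15 = 28.9%.
- Simulating 58 over four strata with incomplete last blocks gives 30.4 to 30.5% under all three share patterns.

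**Best guess, blocks of 4.** The rule is to guess the code used less so far in the stratum.
- By position, the chance of being right is 1/2, 2/3, (1/3)(1) + (2/3)(1/2) = 2/3, 1. The sum is 2.833 of 4 = 70.8%, against 50% by chance.
- With 15 in a stratum: (3×2.833 + 1.833)/15 = 68.9%.

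**After the fix.** I simulated 15 per stratum with sizes drawn at random with equal probability. The observer knows the possible sizes but not which was drawn, and a code counts as certain only if its probability given the history is 1.

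| Block sizes | Certain | Best guess right |
|---|---|---|
| 4 only | 29% | 69% |
| 4 and 6 | about 6% | about 67.5% |
| 4, 6 and 8 | 2 to 3% | about 66% |

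**Overall imbalance, blocks of 4**
- During accrual: 4 strata × 2 = 8.
- At 58: a difference of 8 needs every stratum to stand two past a multiple of 4. The total would then be divisible by 4, and 58 is not. Three such strata with the fourth complete is possible, giving 6.
- Simulated chance that the difference exceeds 2 at 58: 7.6 to 8.5% across the three share patterns.
- Efficiency relative to an equal split is 4·n₁·n₂/N². At the worst case, 32/26: 4×32×26/58² = 3328/3364 = 98.9%.

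**The case against.** The strongest reply is that several things must go wrong together before any bias arises.

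- **The size is inferred.** The words fixed and 4 do not appear, and nothing says the coordinator is told the size. A mixture of 2s and 4s would also respect a limit of 2. This stands as a caution, but equating 2 with half of a single *b* most naturally gives 4.
- **Only a letter is foreseeable.** The key is hidden, and placebo and NR are both blue powder in blue capsules. The pilot adverse-event table in Section 6 shows no pattern that would betray NR: 9 reports on placebo against 5 on NR, with flushing 2 against 1. This stands. A reader might infer that staff could predict the treatment, and might cite the visit table, which prints Group A beside NR and Group B beside placebo. That table can equally be read as illustration, and the randomization text says the identities are masked, so the stronger reading is not supported.
- **The stratum is unknown at recruitment.** APOE status comes from blood drawn after consent. Foreknowledge is therefore confined to the window between genotyping and assignment, by which time a nurse practitioner has reviewed the laboratory results and the PI decides eligibility. This narrows the opportunity. It does not close it, because some eligibility decisions involve judgement and the PI also holds the emergency login.
- **The remedy barely changes the best guess.** This is true. Guessing the code used less so far needs no knowledge of block size. What the remedy removes is most of the certainty.
- **The imbalance is harmless.** This is true for power. A reader might also quote a larger figure at 73, but 73 allows for failed screens and only those who qualify are randomized, so it is not a randomized number. At any odd total, moreover, exceeding 2 mostly means a difference of 3.

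**Conclusion.** The point holds as a modest weakness in allocation concealment plus one inaccurate sentence. With blocks of 4, an observer who tracks assignments by stratum could be certain of about 30% of codes at the planned size. The range is 28.9% to 30.5% depending on how the strata fill, and 33.3% for complete blocks. This rests on the deduced block size, on crossed strata, and on the coordinator seeing past codes. It becomes knowledge of treatment only if A and B are decoded. Nothing in the documents suggests that this has happened or that anyone has exploited the pattern.

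The limit of 2 is right within a stratum and wrong overall, where 8 is possible during accrual and 6 at 58. A reader might infer that the trial could lose power through unequal groups. The 98.9% efficiency in the worst case at 58 rules that out. Both parts are worth correcting because the cost is small; neither undermines the design.

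**What to change.** For participants not yet randomized, have the biostatistician generate and upload a new list with block sizes drawn at random within each stratum, for example 4 and 6. Remove the size, and any limit from which it can be deduced, from the protocol. Keep it from the coordinator and the PI in a document held by the biostatistician. Retain block identifiers there so that the block indicators planned in Section 10 can still be fitted.

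Replace the balance sentence with one saying that imbalance is limited within each stratum of sex and APOE ε4 status, and that the overall difference may be larger. If a figure is wanted for the scheme used so far, it can be reported after the trial.

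The cost is one REDCap upload and one sentence. The downside is a slightly looser limit: with blocks of up to 6 it is 3 per stratum and 4×3 = 12 overall, instead of 2 and 8. Even a 35/23 split at 58 would keep 4×35×23/58² = 3220/3364 = 95.7% efficiency, and differences of that size would be rare. The change leaves the two shared codes in place, so the consequence of a single unblinding is unchanged.
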